9.5. VITAL SIGNS

Vital signs will be measured at the screening visit (Week -2 to -5), at week 0, 6, 12, 24, 36, 48 from screening to week 48, at every 24 weeks after week 48 to end of study, at end of treatment visit and follow up (4 weeks after end of treatment visit) visit.

Measurements of vital signs will include measurement of supine, sitting and standing blood pressure (BP) measurements, and heart rate. Only the BP measured in the sitting position will be used to determine eligibility. Orthostatic systolic and diastolic BP will be calculated as supine measurement - standing measurement.

For BP, pulse rate, and respiration rate, observed values and change from baseline will be summarized by treatment arm and nominal visit using descriptive statistics (n, mean and median, standard deviation, Q1, and Q3, minimum and maximum). For BP, supine, sitting, standing, and orthostatic BP will be summarized. Summary will also be conducted for subjects who have been prescribed insulin or sulfonylurea to control their diabetes.

9.6. ELECTROCARDIOGRAM

A 12-lead electrocardiogram (ECG) will be conducted at the screening visit (Week -2 to -5), at week 0, 6, 12, 24, 36, 48 from screening to week 48, at every 24 weeks after week 48 to end of study, at end of treatment visit and follow up (4 weeks after end of treatment visit) visit. ECG parameters measured will be the RR interval, PR interval, QRS duration, and QT interval. Each ECG should also be assessed by the investigator for signs of ischemia, clinically significant hypertrophy, and clinically significant T-wave abnormalities or arrhythmia.

If a subject's ECG parameters cannot be determined due to pacemaker placement or atrial fibrillation, the ECG parameters will be considered missing. Any machine generated values such as negative values, 0, or 9999 will be excluded from the analyses.

For each abnormal ECG result, the investigator shall ascertain if the observation represents a clinically significant change from the screening ECG for that individual subject (this determination, however, does not necessarily need to be made the first time an abnormal result is observed. The investigator may repeat the ECG to verify the results of the original result). If the ECG result is determined to be a clinically significant and abnormal change from baseline for that subject, it is considered an AE.

For the ECG parameters, observed values and change from baseline from scheduled visits will be summarized with descriptive statistics by treatment arm and overall at each visit. The maximum change from baseline from scheduled visits will also be provided for ECG parameters.

For the ECG overall assessment, the number and percentage of subjects in each overall assessment category (normal, abnormal but not clinically significant, abnormal and

clinically significant, missing) will be presented by treatment arm and overall at each visit.

10. INTERIM ANALYSES

No interim analyses are planned.

11. DATA AND SAFETY MONITORING BOARD

An independent data and safety monitoring board (DSMB) will review descriptive summaries of accumulating safety, subject disposition and limited efficacy data every 6 months, or a frequency recommended by the DSMB.

A designated statistician who is not involved with the study operation will hold the treatment codes. The unblinded treatment information can be provided to the DSMB to facilitate the evaluation of any clinically important increase in the rate of a serious suspected adverse reaction or to the designated safety contact when the treatment information is required to determine if an expedited safety report must be submitted to regulatory agencies. The data outputs for this review will be created by an unblinded team. Personnel involved in the conduct of the study will not participate in the preparation of these outputs, receive the data, or participate in the unblinded portions of the DSMB meetings. More details will be provided for DSMB charter and DSMB SAP.

12. CHANGE FROM ANALYSIS PLANNED IN PROTOCOL

In protocol, per protocol Analysis Set will include all subjects in the Full Analysis Set (FAS) who meet the study eligibility requirements and have no major protocol deviations that will affect the validity of the efficacy measurements. FAS is changed to ITT.

In all analysis models, randomization stratification factors are used as covariates in the protocol. In SAP, baseline eGFR group and continuous baseline HbA_{1c} are used, instead of screening eGFR groups and screening HbA_{1c} groups.

In protocol, primary analysis of the primary endpoint is MMRM using all available data. This has been updated to use imputed data based on retrieval dropout subjects.

Exploratory object below is added:

- To compare the time to hospitalization for a heart failure event or a cardiovascular death.
- To assess the effect of bexagliflozin compared to placebo on the change in HbA_{1c} from baseline to week 24 in randomized subjects who have been prescribed sulfonylurea without insulin to control their diabetes.

Exploratory endpoint below is added:

- Time to hospitalization for heart failure or cardiovascular death in subjects in all subjects and in subjects with a history of heart failure.
- Change in HbA_{1c} from baseline to week 24 in randomized subjects who have been prescribed sulfonylurea without insulin to control their diabetes.

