9.6 Secondary Endpoints

9.6.1 Key Secondary Efficacy Endpoints

The key secondary efficacy endpoints include:

- Change in HbA1c from baseline to week 24 in randomized subjects who have been prescribed insulin to control their diabetes
- Change in body weight from baseline to week 48 in subjects with a BMI ≥ 25 kg/m²
- Change in SBP from baseline to week 24 in subjects with baseline systolic blood pressure ≥ 140 mmHg

It is anticipated that approximately 50% of the randomized subjects will have been prescribed insulin to manage their disease. The sample size for the key secondary efficacy end point to evaluate the treatment effect of bexagliflozin compared to placebo on the change in HbA1c from baseline to week 24 in subjects who have been prescribed insulin to control their diabetes is estimated to be 800. For this key secondary endpoint, the estimated sample size will yield >90% power to detect a treatment effect of 0.3% assuming the SD is 1.1% for a two-sided superiority testing.

It is also anticipated that a high proportion of the randomized subjects would have a baseline BMI ≥ 25 kg/m² and baseline SBP ≥ 140 mmHg in this cardiovascular risk enriched population for the analysis in change in body weight and change in SBP.

A hierarchical testing procedure will be applied to these endpoints in the sequence provided above. These key secondary endpoints will only be tested sequentially when significant treatment differences are established for the primary efficacy endpoint in the comparisons between bexagliflozin and placebo.

The comparison between treatment populations at week 24 (HbA1c and SBP) or 48 (body weight) will be carried out using an MMRM ANCOVA model with unstructured covariance assumption. The model will include terms for treatment, randomization stratification factors, visit, and treatment-by-visit interaction as fixed effects and the corresponding baseline value as an additional fixed effect covariate. Treatment comparison p-values and the difference at week 24 (HbA1c and SBP) or 48 (body weight) will be estimated from the model, with the two-sided 95 % CIs of the difference also presented. If the model does not converge with the unstructured correlation assumption, an autoregressive (1) covariance structure will be used.

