9.6.2 Exploratory Efficacy Endpoints

The exploratory secondary efficacy endpoints include:

- Change from baseline in HbA1c over time
- Change from baseline in FPG over time
- Change from baseline in body weight over time
- Change from baseline in SBP over time
- Requirement of additional anti-diabetic medications, including insulin; and time to first use of additional anti-diabetic medication
- Requirement of reduced anti-diabetic medications, including insulin dose over time
- Hospitalization for heart failure in all subjects and in subjects with a history of heart failure
- time to hospitalization for heart failure in subjects in all subjects and in subjects with a history of heart failure

For changes from baseline in HbA1c, FPG, body weight, and SBP over time, a similar MMRM ANCOVA model will be used as for the key secondary efficacy endpoints. Of interest in the MMRM ANCOVA model is the difference between treatments on these endpoints across all post-baseline time points. Also, changes from baseline for each endpoint will be estimated and analyzed at each study visit using this MMRM model. Specifically, for each endpoint, treatment difference in least squares means will be estimated by visit from the model with the corresponding p-values and the two-sided 95% CIs of the difference between treatments.

Endpoints measuring proportions over time will be analyzed using generalized estimating equation (GEE) logistic regression using similar independent variables as the MMRM ANCOVA models above (the treatment-by-visit interaction term will be removed if not significant), and using an unstructured correlation structure (or autoregressive(1) if the model with the unstructured structure does not converge). Of interest is the difference between treatments across all post-baseline time points. Also, odds ratios will be estimated from the model with the corresponding p-values and their two-sided 95% CIs presented at each visit. For time-to-event endpoints, Cox proportional hazards models with treatment and randomization stratification factors as the covariates will be used to estimate the hazard ratio of the endpoint, p-value and its two-sided 95% confidence interval comparing bexagliflozin to placebo. Subjects who withdraw from the trial and for whom no follow up event data are collected (i.e., lost to follow-up subjects) will be censored at the last known follow-up.

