3.8. TREATMENT ASSIGNMENT & BLINDING

3.8.1. Treatment Assignment

Potential study subjects will be screened and assigned a subject number. Once all screening procedures are completed and the study eligibility is confirmed by the investigator, the randomization numbers will be allocated to subjects within the appropriate treatment arm by the randomization system. Once a screening or randomization number has been assigned, it will never be re-used. No subjects will be randomized into the study more than once. If a randomization number has been allocated incorrectly, no attempt will be made to remedy the error once study medication has been dispensed. The subject will continue with the randomization number and study medication. The study staff will notify the Sponsor Contact as soon as the error is discovered without disclosing the study medication administered. Admission of subsequent eligible subjects will continue using the next unallocated number in the sequence.

The study will be conducted at investigative sites in multiple countries and will likely involve variable numbers of subjects at each site. Enrollment will be on a competitive basis but each site will be capped at 48 subjects per site. Activation of investigational sites in each country will be centrally controlled by a centrally managed Interactive Web Response system (IWRS).

Eligible subjects who complete the run-in period and meet all study inclusion/exclusion requirements will be randomized in a 2:1 ratio to receive investigational product. Subjects will be assigned to treatment arms in sequential order as they qualify for the study, using the IWRS. Randomization will be stratified according to baseline HbA_{1c} ($\leq 9.5\%$ or $> 9.5\%$ at screening visit), baseline eGFR (eGFR < 60 or ≥ 60 mL min⁻¹ per 1.73 m² at screening), BMI (< 25 kg m⁻² or ≥ 25 kg m⁻²) and history of heart failure (yes or no).

Among the 3 groups of subjects based on the baseline CV risks, a minimum of 352 subjects (21%) from each of the three groups will be recruited and ≤ 400 subjects who have a history of heart failure can be randomized in the study. If a subject has a history of class

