This will be tested if the primary efficacy endpoint and the key secondary endpoint-change from baseline HbA_{1c}, overall and in subjects prescribed with insulin, are significantly different between bexagliflozin and placebo groups based on ITT analysis set. Change from baseline in body weight at week 48 will be analyzed using the MMRM ANCOVA model with unstructured covariance assumption. The model will include terms for treatment, visit, treatment-by-visit interaction, baseline HbA_{1c}, region, baseline eGFR categories (<60 or ≥ 60 mL min⁻¹ per 1.73 m²), baseline BMI ($<$ or ≥ 25 kg m⁻²), and history of heart failure (yes or no), insulin use or not as fixed effects and the corresponding baseline body weight value as an additional fixed effect covariate. Treatment comparison p-values and difference at week 48 will be estimated from the model, with the two-sided 95% CIs of the treatment difference also presented. If the model does not converge with the unstructured correlation assumption, an autoregressive AR(1) model will be used. If the primary hypothesis or treatment effect on HbA_{1c} for subjects prescribed with insulin is not significant, the nominal p-value will not be used for inferential purposes. Analysis will also be conducted for subjects who have been prescribed insulin or sulfonylurea to control their diabetes.

8.2.1.3. Change in SBP from baseline to week 24 in subjects with baseline SBP ≥ 140 mm Hg

This will be tested if the primary efficacy endpoint and the key secondary endpoints - change from baseline HbA_{1c} for subjects prescribed with insulin, and change from baseline body weight are significant. Change from baseline in sitting SBP at week 24 will be analyzed using the MMRM ANCOVA model with unstructured covariance assumption. The model will include terms for treatment, region, baseline eGFR categories (<60 or ≥ 60 mL min⁻¹ per 1.73 m²), baseline BMI ($<$ or ≥ 25 kg m⁻²), and history of heart failure (yes or no), insulin use or not, visit, treatment-by-visit interaction, baseline HbA_{1c} as

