8.2.2.2. Changes from baseline in HbA_{1c} and FPG over time

Of interest is the difference between treatments on these two endpoints across all post-baseline time points with sufficient number of values. If for any treatment arm, less than 20 subjects completed the assessment in the analysis visit window, the visit will not be included in the analysis. Both endpoints will be analyzed using MMRM model with the change from baseline values across all post-baseline visits used as dependent variable. The fixed effect will include baseline eGFR (≥ 60 or < 60 mL min⁻¹ [1.73m]⁻²), baseline BMI ($<$ or ≥ 25 kg m⁻²), and history of heart failure (yes or no), insulin use or not, treatment, visit, treatment and visit interaction, other hypoglycemic agent use (no change, after relaxation, or after intensification), treatment and other hypoglycemic agent use interaction, and baseline value. For each endpoint, treatment difference in least squares means will be estimated by visit from the model with the corresponding p-values and the two-sided 95% CIs of the difference between treatments.

Analysis of HbA_{1c} over time will also be conducted for subjects who have been prescribed insulin or sulfonylurea to control their diabetes.

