8.2.2.3. Changes from baseline in SBP and weight over time

Both endpoints will be analyzed using MMRM model with the change from baseline values across all post-baseline visits used as dependent variable. The fixed effect will include baseline eGFR (≥ 60 or < 60 mL min⁻¹ [1.73m]⁻²), baseline BMI ($<$ or ≥ 25 kg m⁻²), and history of heart failure (yes or no), insulin use or not, treatment, visit, treatment and visit interaction, and baseline value. For each endpoint, treatment difference in least squares means will be estimated by visit from the model with the corresponding p-values and the two-sided 95% CIs of the difference between treatments.

8.2.2.4. Proportions of subjects with intensification and relaxation of hypoglycemic agent (i.e. requirement of additional anti-diabetic medications and with requirement of reduced anti-diabetic medications)

These endpoints will be analyzed using logistic regression. The model will include terms for treatment, region, baseline eGFR categories (<60 or ≥ 60 mL min⁻¹ per 1.73 m²), baseline BMI ($<$ or ≥ 25 kg m⁻²), and history of heart failure (yes or no), insulin use or not,

and baseline HbA_{1c}. The LS mean proportions and the two-sided 95% CI for each treatment will be presented. Also, odds ratio of treatment difference of bexagliflozin group over the placebo group will be estimated from the model with the corresponding p-values and their two-sided 95% CIs presented. Analysis will also be conducted for subjects who have been prescribed insulin or sulfonylurea to control their diabetes.

8.2.2.5. Proportions of subjects with hospitalization of heart failure in all subjects, with hospitalization of heart failure in subjects with a history of heart failure

These endpoints will be analyzed using logistic regression. The model will include terms for treatment, region, baseline eGFR categories (<60 or ≥60 mL min⁻¹ per 1.73 m²), baseline BMI (< or ≥25 kg m⁻²), history of heart failure (yes or no), insulin use or not, and baseline HbA_{1c}. Odds ratios will be estimated from the model with the corresponding p-values and their two-sided 95% CIs. The odds ratios of bexagliflozin group over the placebo group will be estimated from LS means based on the model with the corresponding p-values and their two-sided 95 % CIs presented.

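### The over-time models for FPG, SBP and body weight leave out HbA1c, a randomization stratification factor, and SAP section 12 does not declare the exception

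*Combined protocol and SAP*

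**What the plan says.** Randomization is stratified by four factors: HbA1c, eGFR, BMI and history of heart failure (protocol 5.4, SAP 3.8.1). Region is not one of them.

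For changes over time in HbA1c, FPG, body weight and SBP, protocol 9.6.2 states that "a similar MMRM ANCOVA model will be used as for the key secondary efficacy endpoints". Protocol 9.6.1 defines that key secondary model: "The model will include terms for treatment, randomization stratification factors, visit, and treatment-by-visit interaction as fixed effects", with the endpoint's own baseline as a further covariate.

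SAP section 12, which records departures from the protocol, says "In all analysis models, randomization stratification factors are used as covariates in the protocol". It continues: "In SAP, baseline eGFR group and continuous baseline HbA_{1c} are used, instead of screening eGFR groups and screening HbA_{1c} groups". This changes the form of two factors. It does not say that either is removed from any model.

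The SAP's over-time models are specified as follows.

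- **8.2.2.2 (HbA1c and FPG):** eGFR group, BMI group, heart failure history, insulin use, treatment, visit, treatment by visit, other hypoglycemic agent use, then "treatment and other hypoglycemic agent use interaction, and baseline value".
- **8.2.2.3 (SBP and body weight):** eGFR group, BMI group, heart failure history, then "insulin use or not, treatment, visit, treatment and visit interaction, and baseline value".

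By contrast, the key secondary body weight model in 8.2.1.2 lists "treatment-by-visit interaction, baseline HbA_{1c}, region, baseline eGFR categories" among its terms.

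**The concern.** In the over-time models the baseline value is that of the endpoint being analysed. For HbA1c over time it supplies the HbA1c adjustment. For FPG, SBP and body weight it does not, so HbA1c is absent from those three models although section 12 implies that it is present.

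Two things are at stake. First, section 12 is where a reader looks for departures from the protocol, and on this point it does not match the model statements. A programmer working from section 12 and another working from 8.2.2.2 and 8.2.2.3 would fit different models and report different nominal p-values. Second, HbA1c could explain part of the FPG response beyond a single baseline FPG value, so leaving it out might cost some precision.

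**Working it through.** **1. Term-by-term comparison.** Whether baseline HbA1c is in each SAP model:

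| Model | SAP section | Baseline HbA1c |
|---|---|---|
| Primary, HbA1c at week 24 | 8.1.1 | yes |
| Key secondary: HbA1c in insulin users | 8.2.1.1 | yes |
| Key secondary: body weight | 8.2.1.2 | yes |
| Key secondary: SBP | 8.2.1.3 | yes |
| HbA1c over time | 8.2.2.2 | yes, as its own baseline |
| FPG over time | 8.2.2.2 | **no** |
| SBP over time | 8.2.2.3 | **no** |
| Body weight over time | 8.2.2.3 | **no** |
| Logistic models | 8.2.2.4, 8.2.2.5 | yes |
| Cox models | 8.2.2.6, 8.2.2.7 | yes |
| UACR | 9.4 | yes |

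The eGFR group, BMI group and heart failure history are in all three models marked no. HbA1c is the only stratification factor missing.

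**2. Does the omission damage inference?** The FPG case was simulated as a single-visit ANCOVA with 1650 subjects, 2:1 allocation in permuted blocks within HbA1c strata, no treatment effect, and adjustment for baseline FPG. Each setting had 4000 runs. The baseline correlation of FPG and HbA1c was set at 0.6. The partial correlation r of HbA1c with the outcome, given baseline FPG, was varied. All of these correlations are assumptions.

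| r | Type I error without HbA1c | Type I error with HbA1c |
|---|---|---|
| 0 | 4.6% | 4.6% |
| 0.1 | 5.2% | 5.0% |
| 0.2 | 4.9% | 5.3% |
| 0.3 | 4.6% | 4.7% |

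The Monte Carlo standard error is √(0.05 × 0.95 / 4000) = 0.34 percentage points, so no entry is distinguishable from 5%. Mean estimates were within 0.002 outcome SD units of zero throughout.

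**3. How much precision could FPG gain?** The documents give neither an FPG standard deviation nor an FPG–HbA1c correlation, so two assumed ranges are used. Adding a covariate with partial correlation r reduces the standard error by 1 − √(1 − r²):

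- r = 0: 0%
- r = 0.1: 1 − √0.99 = 0.5%
- r = 0.2: 1 − √0.96 = 2.0%
- r = 0.3: 1 − √0.91 = 4.6%

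The second route is a measurement-error model. Let T be true glycemia, baseline FPG = T + e, HbA1c in glucose units = T + a, and later FPG = bT + u + e′. With k = V(T)V(e) / [V(T) + V(e)], the partial R² of HbA1c given baseline FPG is

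b²k² / {[k + V(a)] × [b²k + V(u) + V(e)]}.

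Assumed ranges: SD(T) 35–45, SD(e) 20–40 and SD(a) 20–40 mg/dL, b 0.5–0.7, SD(u) 0.5–0.8 times SD(T). These imply a baseline FPG–HbA1c correlation of 0.43 to 0.84.

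- **Largest gain** (SD(T) 45, SD(e) 40, SD(a) 20, b 0.7, SD(u) 22.5): k = 2025 × 1600 / 3625 = 893.8. R² = 0.49 × 893.8² / [1293.8 × (438.0 + 506.3 + 1600)] = 11.9%. Standard error reduction: 1 − √0.881 = 6.1%.
- **Smallest gain** (SD(T) 45, SD(e) 20, SD(a) 40, b 0.5, SD(u) 36): k = 2025 × 400 / 2425 = 334.0. R² = 0.25 × 334.0² / [1934.0 × (83.5 + 1296 + 400)] = 0.8%. Standard error reduction: 0.4%.
- **Median** over low, middle and high values of each input: R² = 4.0%, a standard error reduction of 2.0%.

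The two routes together span roughly 0% to 6%.

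**4. SBP and body weight.** The partial R² of HbA1c is assumed to be below 1%, so the standard error gain is below 1 − √0.99 = 0.5%.

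**The case against.** The strongest reply is that this is a documentation mismatch in exploratory models on which no decision depends. SAP 8.2.2 says these endpoints carry nominal p-values, used only to look for trends. Protocol 9.6.2 promises a similar model, not an identical one. Section 12 is not a complete covariate inventory: it does not mention insulin use or region, which other SAP models carry. The revision history has a general entry about corrections to model covariates, so a deliberate choice cannot be excluded. All of this stands, and it sets the importance of the point. It does not remove the gap: section 12 speaks of all analysis models, keeps HbA1c in baseline form, and gives neither an exception nor a reason for these three.

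A reader might also infer more than the documents support:

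- **That standard errors or p-values are invalid.** The simulation of the FPG case shows neither bias nor type I error inflation.
- **That FPG precision is definitely lost.** Every input to that calculation is assumed, and zero loss is within the range. The measurement-error calculation also ignores insulin use, eGFR and other hypoglycemic agent use. These are already in the FPG model and may absorb part of what HbA1c would explain.
- **That region is a second dropped randomization factor.** It is absent from all four over-time models, but it is not a stratification factor, and neither section 12 nor the protocol model for these endpoints promises it.
- **That the over-time weight and SBP estimates should match the key secondary ones.** The key secondary analyses are restricted to BMI of at least 25 kg/m² and to baseline SBP of at least 140 mmHg, and the SBP analysis stops at week 24. The estimates would differ even with identical covariates.

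**Conclusion.** The point holds as a narrow one. Three exploratory over-time models (FPG, SBP and body weight) omit one of the four stratification factors while keeping the other three, and section 12 does not declare it. This is an undeclared departure from the protocol's model.

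The consequence is small. The possible gain from restoring HbA1c is about 0% to 6% of the FPG standard error, and under 0.5% for SBP and body weight. Both figures rest on assumed correlations, because the documents supply none. The validity result comes from a single-visit simulation of the FPG case. The primary and key secondary analyses already include baseline HbA1c and are unaffected.

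**What to change.** Add continuous baseline HbA1c as a fixed-effect covariate to the FPG model in SAP 8.2.2.2 and to the SBP and body weight models in SAP 8.2.2.3, before unblinding. The HbA1c over-time model needs no such change. This brings the three models into line with section 12 and with the rest of the SAP.

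If the omission was intended, section 12 should instead list these three models as an exception and give the reason. That would cure the mismatch but not recover any precision.

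Adding region to the four over-time models is optional, for consistency with the other SAP models only.

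The cost is one term in existing model code, a negligible loss of degrees of freedom, and no new data.
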